4.2.1 Patient Disposition

The end of study status for each patient stating whether or not they completed the study protocol will be listed. The listing will also include the date of completion or premature discontinuation, the study day patient discontinued, the primary reason for discontinuation, and if applicable, the date and cause of death and whether an autopsy was performed or not.

The number of patients screened, enrolled, treated and the frequency and percentage of patients completing the study, patients withdrawing prematurely, and primary reason for withdrawal will be summarized by dose level.

4.2.2 Analysis Datasets

The number and percentage of subjects in each analysis set will be summarized by dose level. Whether or not each subject was included in each of the analysis data sets will be indicated in a listing.

4.2.3 Informed Consent and Enrollment

A listing will display the date and time the patient signed the informed consent and the date of enrollment. In addition, a listing for optional consents will be displayed for each patient.

- Tumor tissue biopsies (one month after treatment) collection
- Archived tumor tissue collection
- Photograph collection (from injected tumor)
- Storage for future use of samples of blood, and/or tissue for other tests (not genetic)
- Storage for future use of samples of blood, and/or tissue for other tests (genetic)
- Storage for future use of information/data resulting from analysis of patient's samples

4.2.4 Inclusion/Exclusion Review

Whether the patient met all inclusion criteria, none of the exclusion criteria, and any inclusion criteria not met or exclusion criteria met at screening will be listed.

4.2.5 Blood Type Results Pre-dose

Results of the assessment for patient blood type will be listed.

4.2.6 **Pregnancy Tests**

Whether a female patient is of childbearing potential and results of any pregnancy testing at Screening and Day 0 will be listed.

4.2.7 Demographics

The following demographic information collected at screening will be listed: sex, race, ethnicity, age, body weight, and height at screening.

Descriptive statistics will be calculated by dose level for the continuous variables age, body weight, and height. Frequencies and percentage of patients will be tabulated by dose level for the categorical variables collected at screening: ethnicity, race, and sex.

4.2.8 Medical History and Current Medical Conditions

All relevant medical history and current medical conditions collected at Screening and Day 0 until the start of the IMP will be listed for each patient.

Medical History conditions will be coded using the Medical Dictionary for Regulatory Activities (MedDRA), Version 14.1. The MedDRA preferred term and system organ class of the medical history/condition will also be listed.

The number and percentage of subjects with medical history/current medical condition at the start of IMP administration will be summarized by dose level, system organ class, and preferred term at screening and day 0.

4.2.9 **Prior Cancer History**

A listing will present the diagnosis, date of initial diagnosis, histology, primary site at diagnosis, initial staging of the tumor size, lymph nodes, and metastasis, date of initial diagnosis of metastasis, and the current extent of disease.

Prior diagnostic and therapeutic procedures for cancer including the procedure, date, purpose, and findings will be presented in a listing.

Prior systemic anticancer therapies, including regiment number, drug, intent, dose, unit, date started and stopped, number of cycles, frequency of cycles, best response, reason for discontinuation, and date of progression will be presented in a listing.

A listing will contain prior cancer radiotherapies, including regimen number, location, radiotherapy field of treatment, intent, date of first and last fraction, total dose, and best response.

4.2.10 Brain MRI

Date of the brain MRI, indication of metastatic disease, and MRI findings and comments will be listed for each patient.

4.2.11 Echocardiogram (ECHO)

The date of the ECHO and whether or not the ECHO met the exclusion criteria will be listed.

4.2.12 Twelve-Lead Electrocardiograms (ECG)

Descriptive statistics will be calculated by dose level for the continuous variables QTcB, QTcF, PR, RR, QRS and HR at screening and Day -1 to Day 0 pre-dose.

Date and time of ECG, overall assessment, ECG abnormalities, and ECG parameters including QTcB, QTcF, RR, PR, QRS, and HR value taken at Screening and Day -1 to Day 0 pre-dose will be listed.

4.2.13 Study Drug Administration

A listing will present dose level, cohort, patient number, anatomical site of injected tumor, whether the entire amount was given, estimated residual volume, the date and time of dose given, dose administered (units), total number of spores injected or administered, any problem with the injection, any pre-med given, whether the injection was performed using re-direction technique, how many re-directions, whether a needle was used or an alternate injection device, description of an alternate device was if used, needle gauge, needle size, syringe size, any radio guidance used for injection and any comments. Actual dose received will be summarized descriptively by dose level.

4.3 Efficacy Analysis

Results of the CT and/or MRI scans will be listed by dose level and time points for each patient.

Results of the injection lesion evaluation, the overall response assessment, and the best overall response assessment per RECIST will be listed by dose level and time points.

Summary table for individual patient data for injection lesion measurements will present descriptive statistics by dose level and time point for the lesions' longest diameter (cm),

including % reduction in injection lesions' longest diameter (cm) from baseline and nadir.

The overall lesion response will be summarized using the number and percentage of patients by dose level and time point within each of the categories: complete, partial, stable, progressive, or unknown.

The best overall lesion response will be summarized using the number and percentage of patients by dose level within each of the categories: complete, partial, stable, progressive, or unknown.

4.4 Pharmacodynamics Analysis

4.4.1 Anti-C. novyi-NT Immune and Inflammatory Response

All data collected to assess the immune and systemic inflammatory responses during *C. novyi*-NT treatment (CRP, IL-6, IL-8, TNF-alpha, etc.) will be the responsibility of BioMed Valley Discoveries.

4.4.2 *C. novyi*-NT Detection in Circulation and/or abscess material/postdose tumor sample

Results from tumor biopsy assessments will be listed for each patient over time. Information presented will include the date and time of collection, days after IMP administration, anatomical location, and present the following for both anaerobic and aerobic culture: date and time of culture, days after IMP administration, culture results (positive/negative), whether bacteria was found (Yes/No), and if bacteria was found does the bacterial growth represent an infection or contamination.

Results will be summarized to show the number and percentage of patients.

Results from abscess material assessments will be listed for each patient over time. Information presented will include the type of material collected and volume, location (if other, specify non-injected lesion number or anatomical site), days after IMP administration, and present the following for both anaerobic and aerobic culture: date and time of culture, days after IMP administration, the culture result (presence or not), whether bacteria was found (Yes/No), and if bacteria was found does the bacterial growth represent an infection or contamination.

Blood culture and abscess results will be summarized to show the number and percentage of patients with presence of *C. novyi*-NT.

4.5 Safety Evaluation

4.5.1 Adverse Events (AEs)

Adverse Events will be mapped to the Medical Dictionary Regulatory Activities (MedDRA), Version 14.1 with the lowest level term that most accurately reflects the adverse event.

Adverse events will be categorized as:

- Treatment emergent adverse event (TEAE): A treatment-emergent adverse event is defined as any event not present prior to the initiation of the treatments or any event already present that worsens in either intensity or frequency following exposure to the treatments.
- Non-treatment emergent adverse events (NTEAE): An AE that occurred before the first administration of IMP and did not worsen in severity or frequency after IMP exposure.

All adverse event data recorded on the eCRFs will be listed by dose level and patient. Included on the AE listing will be the adverse event, start date and time, outcome, stop date and time, CTCAE grade, relationship to study drug, action taken, whether the AE was serious, whether TEAE, whether or not a concomitant medication was taken, time of AE onset relative to IMP dosing and AE duration.

All serious adverse events will be listed. A listing of all AEs leading to treatment discontinuation will be presented. Details of death and hospitalization relating to serious adverse events will be listed.

As defined in the protocol, all adverse events will be assigned a CTCAE grade of 1 to 5.

Unless specified otherwise, all adverse event summaries will include the TEAEs only. In these summaries the count of AEs will be the number of patients reporting adverse events and not the number of events reported. If the same AE (preferred term) is reported several times for the same patient, it will only appear once for that specified dose level in the summary tables. For patients with multiple adverse events of the same preferred term and of different intensity, the highest intensity assessment will be used in summaries presented by intensity.

For purposes of the summary tables, AEs will be classified as either being related to IMP or not related. AEs related to IMP will include AEs classified as 'Definite', 'Probable', or 'Possible'. AEs not related to IMP will include AEs classified as 'Not Related' or 'Unlikely'.

Frequency counts will be categorized and displayed by the MedDRA system organ class and preferred term.

An overview table will be presented by dose level and overall. This summary will present the number and percentage of patients, as well as number of events with treatment emergent: AEs; SAEs; AEs related to IMP; SAEs related to IMP; AEs leading to discontinuation of IMP; AEs by CTC Grade; and AEs with CTC Grade 3 or higher.

Other summary tables for adverse events will include:

- 1) Number and Percentage of Subjects with Treatment Emergent Adverse Events by System Organ Class, Preferred Term, and Dose Level
- 2) Number and Percentage of Subjects with Treatment Emergent Adverse Events 'Related to IMP' by System Organ Class, Preferred Term, and Dose Level
- 3) Number and Percentage of Subjects With Serious Treatment Emergent Adverse Events by System Organ Class, Preferred Term, and Dose Level
- 4) Number and Percentage of Subjects With Serious Treatment Emergent Adverse Events 'Related to IMP' by System Organ Class, Preferred Term, and Dose Level
- 5) Number and Percentage of Subjects with Treatment Emergent Adverse Events 'Related to IMP' by System Organ Class, Preferred Term, CTCAE Grade, and Dose Level
- 6) Number and Percentage of Subjects with Treatment Emergent Adverse Events 'Not Related to IMP' by System Organ Class, Preferred Term, CTCAE Grade, and Dose Level
- 7) Number and Percentage of Subjects with Treatment Emergent Adverse Events with Frequency >=2 Patients by Preferred Term
- 8) Number and Percentage of Subjects With Serious Treatment Emergent Adverse Events by Preferred Term

Above tables 1) - 4) present columns of Any grade and Grade ≥ 3 for each dose level, any grade includes missing grade; tables 5) and 6) present each available grade at each dose level; tables 7) and 8) present number of patients and number of events at each dose level by descending frequency of overall dose.

4.5.2 Clinical Laboratory

Routine hematology, chemistry and coagulation laboratory assessments will be provided in listings respectively. These listings also include the columns of normality/abnormality and change from baseline except the assessments in CRF. Laboratory values considered to be clinically significant will be listed.

Figures will be used to visualize the change from baseline values of all routine hematology, chemistry and coagulation laboratory assessments over time for each dose group. Figures considered will include plots of the mean over time for each dose level.

The number and percentage of abnormality with shift categories from normal at baseline to high and from normal at baseline to low for hematology, chemistry, and coagulation laboratory assessments.

Laboratory results will be summarized using Systeme International (SI) units.

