3.5 Sample size

Three to six (3 to 6) patients per cohort will be enrolled until the MTD is reached or until complete germination and tumor regression occurs.

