3.9 Safety Assessments

3.9.1 Adverse Events

An Adverse Event (AE) is any new untoward medical occurrence or worsening of a preexisting medical condition in a clinical investigation subject administered an investigational medicinal product, even if it does not have a causal relationship with that product. Any unfavorable or unintended sign, symptom, or disease temporally associated with the use of the study agent, whether or not it is considered study agent-related will be considered an AE. This includes any newly occurring event or previous condition that has increased in severity or frequency since the administration of the study agent.

Monitoring for AEs will occur from the time of informed consent until the patient completes the study. The post-dosing observation period will begin with an 8-day inpatient stay (Days 0 to 7). This inpatient stay can be extended and requires that at least 2 days elapse from the resolution of any signs of infection or serious AEs (SAEs) before discharge.

All Grade 3 and 4 clinical laboratory results that represent an increase in severity from baseline will be reported as AEs. A Grade 1 or 2 clinical laboratory abnormality should be reported as an AE only if it is considered clinically significant by the investigator.

All AEs, including observed or volunteered problems, complaints, or symptoms from the time of informed consent until 8 weeks post-dose are to be recorded, regardless of causality. After 8 weeks post-dose, only AEs with possible, probable, or definite relationship to the study agent will be reported with follow up as noted above for AEs within the first 8 weeks post treatment.

Adverse events will be evaluated against the baseline history and physical examination and intensity graded using the NCI CTCAE, Version 4.0, which can be accessed at http://ctep.cancer.gov/reporting/ctc.html.

All AEs experienced by a patient, irrespective of the suspected causality, will be monitored until the event has resolved or stabilized, until any abnormal laboratory values have returned to baseline or stabilized at a level acceptable to the PI or local investigator and Medical Monitor, until there is a satisfactory explanation for the changes observed, or until the patient is lost to follow-up.

A Serious Adverse Event (SAE) is any AE, occurring at any dose and regardless of causality that:

• Results in death.

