4.1.2 Data Presentations

Data for all enrolled patients who received any amount of IMP will be presented in the data listings. Table summaries will only include those patients that received IMP.

For those listings or data summaries where baseline and change from baseline measurements will be presented, the last observed measurement prior to dosing on Day 0

will be considered the baseline measurement if collecting at both screening and Day -1 to Day 0 pre-dose.

All pre- and post-dose assessments including all unscheduled assessments will be included in the data listings. For pre-dose assessments, the last assessment (including unscheduled) taken for a time point will be used in the data summaries (summary tables, figures, and statistical analysis); for all post-dose time points, the original assessment for any given time point will be used in the data summaries (summary tables, figures, and statistical analysis).

Continuous data will be described using descriptive statistics: number of observations (N), mean, median, standard deviation (SD), minimum and maximum. Frequencies and percentages will be used for summarizing discrete (categorical) data. The denominator for all percentage, unless otherwise specified, will be the number of patients in a given cohort.

Data that are reported as missing will be excluded from all descriptive and nondescriptive data analysis. Observations that are spurious (extreme relative to the majority of the data) will not be altered or removed from any presentation of the data without agreement from the sponsor.

For data listings, all raw data will be reported/displayed exactly as provided. For summaries of quantitative data, the minimum and maximum value will be reported exactly as the raw data are reported; measures of central tendency (means, medians) will be reported to one more decimal place than the raw data; measures of variance (SD) will be reported to two more decimal places than the raw data.

Unless specified otherwise, data collected over time will be listed by cohort, dose level, patient number, and time point (where applicable). Unless specified otherwise, all tables and figures will be presented by dose level. The Summary of Tables, Figures and Listings in the attachment section might be updated later if needed. In this SAP, treatment will refer to any of the following planned categories of *C. novyi*-NT dose level:

- $1 (x \ 10^4 \text{ spores})$
- $3 (x \ 10^4 \text{ spores})$

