4.5.3 Vital Signs

The observed and change from baseline values for blood pressure (systolic and diastolic), heart rate, respiratory rate, oral body temperature and weight will be listed by dose level, patient, and time point.

Figures will be used to visualize the change from baseline values of all vital sign parameters over time for each dose group. Figures considered will include plots of the mean over time for each dose level.

The number and percentage of abnormality with shift categories from normal at baseline to high and from normal at baseline to low for all vital sign parameters.

The number and percentage of patients who had fever at each temperature category will be provided over time for each dose. Temperature categories will be $38 - <=39^{\circ}C$, $>39 - <=40 \circ C$, $>40 \circ C$.

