6.1 Summary of Tables

Patient Dispositi	ion	
Table 14.1.1.1		All subjects
Table 14.1.1.2		
Demographics a	nd Baseline Characteristics	
Table 14.1.2		
Table 14.1.3.1		
Table 14.1.3.2		
Table 14.1.4.1		Safety
Table 14.1.5.1		
6.1.1 M	edication and Treatment	
Table 14.1.6.1	Injection of C. novyi -NT	Safety
Table 14.1.6.2		Safety
Efficacy and Pha	armacodynamics	
Table 14.2.1.1	Number and Percentage of Patients with Non-injected	FAS
	Lesion Measurements	
Table 14.2.1.2	Number and Percentage of Patients with New Lesion Measurements	
Table 14.2.1.3	Summary of Injected Lesion Measurements at Each TimeFASPoint by Each CohortFAS	
Table 14.2.1.4	Summary of Injection Lesion Response	FAS
Table 14.2.1.5	Summary of Overall Lesion Response FA	
Table 14.2.1.6		
Table 14.2.2.1	able 14.2.2.1 Summary of Positive Anaerobic Blood Cultures – Number and Percentage of Patients with Presence of C. novvi-NT	
Table 14.2.2.2		
Table 14.2.2.3 Time (h) of First and Last Positive C. novyi-NT Blood Culture		Safety
Safety		
Table 14.3.1	Overview of Treatment Emergent Adverse Events	
Table 14.3.2		
Table 14.3.3	Treatment-Emergent Adverse Events 'Related to IMP' by System Organ Class, Preferred Term, and Dose Level	Safety

Table 14.3.4	le 14.3.4 Serious Treatment Emergent Adverse Events by System Organ Class, Preferred Term, and Dose Level	
Table 14.3.5	Serious Treatment Emergent Adverse Events 'Related to IMP' by System Organ Class, Preferred Term, and Dose Level	
Table 14.3.6	Summary of AEs Qualified as Dose Limiting Toxicities by System Organ Class, Preferred Term, CTCAE Grade, and Dose Level	Safety
Table 14.3.7	Treatment Emergent Adverse Events 'Related to IMP' by System Organ Class, Preferred Term, CTCAE Grade, and Dose Level	Safety
Table 14.3.8	Treatment Emergent Adverse Events 'Not Related to IMP' by System Organ Class, Preferred Term, CTCAE Grade, and Dose Level	Safety
Table 14.3.9	Treatment Emergent Adverse Events with Frequency >=2 Patients by Preferred Term	Safety
Table 14.3.10	Serious Treatment Emergent Adverse Events by Preferred Term	Safety
Table 14.3.11	Number of Days of Initial Hospitalization	
Table 14.4.1	Shift in Laboratory Hematology from Baseline to each Time Point	
Table 14.4.2	Shift in Laboratory Chemistry from Baseline to each Time Point	Safety
Table 14.4.3		
Table 14.5.1	Shift in Vital Sign from Baseline to each Time Point	Safety
Table 14.5.2		
Table 14.6.1.1	SOFA Scores – Observed Value Summary	Safety

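### The laboratory and vital-sign shift tables count only shifts from a normal baseline, over the whole cohort and by time point, so they give no per-patient count of worsening

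*SAP*

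**What the plan says.** - **Categories.** SAP 4.5.2 names two laboratory shifts: "shift categories from normal at baseline to high and from normal at baseline to low for hematology, chemistry, and coagulation laboratory assessments". SAP 4.5.3 repeats them for vital signs: "shift categories from normal at baseline to high and from normal at baseline to low for all vital sign parameters". No shift from a low or high baseline is named, and no shift in CTCAE grade.
- **Denominator.** SAP 4.1.2: "The denominator for all percentage, unless otherwise specified, will be the number of patients in a given cohort". Neither 4.5.2 nor 4.5.3 specifies another.
- **Value used.** SAP 4.1.2: "for all post-dose time points, the original assessment for any given time point will be used in the data summaries". Unscheduled values go elsewhere: "All pre- and post-dose assessments including all unscheduled assessments will be included in the data listings".
- **Layout.** The table list in 6.1 has titles such as "Shift in Laboratory Hematology from Baseline to each Time Point". No listed shift-table title mentions a worst post-dose value.
- **Cohort size.** SAP 3.5: "Three to six (3 to 6) patients per cohort will be enrolled".
- **Related adverse event rule.** SAP 3.9.1: "All Grade 3 and 4 clinical laboratory results that represent an increase in severity from baseline will be reported as AEs". Grade 1 or 2 laboratory abnormalities are adverse events only if the investigator considers them clinically significant.

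**The concern.** Safety is the first objective in SAP section 2, and results are read by dose level. A shift table should show how many patients got worse and from what starting point. Here three rules act together.

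1. A patient abnormal at baseline has no cell to move into, so a high value that rises further is never counted.
2. That patient still sits in the denominator, as does a patient no longer measured at a late visit.
3. Only the original value at each time point is used, and each time point is tabulated separately. A repeat value does not enter the table, and the number of patients ever abnormal cannot be read from it.

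The SAP's adverse event rules in 4.5.1 take the opposite approach: they count worsening of a pre-existing event and use the highest intensity per patient. The shift tables do neither.

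**Working it through.** The SAP states no rate on this point, so there is no figure to reproduce. The checks below use the planned cohort sizes of 3 and 6 (SAP 3.5) with assumed counts, because the SAP gives no baseline abnormality rate.

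**Ceiling and denominator.** Let n be the cohort size, a the number abnormal at baseline and s the number who shift from normal. The table prints s/n. The rate among patients who can shift is s/(n − a). The largest value that can be printed is (n − a)/n.

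| n | a | s | printed s/n | among those normal at baseline | ceiling |
|---|---|---|---|---|---|
| 3 | 1 | 1 | 1/3 = 33.3% | 1/2 = 50.0% | 2/3 = 66.7% |
| 3 | 2 | 1 | 1/3 = 33.3% | 1/1 = 100% | 1/3 = 33.3% |
| 6 | 3 | 1 | 1/6 = 16.7% | 1/3 = 33.3% | 3/6 = 50.0% |
| 6 | 3 | 2 | 2/6 = 33.3% | 2/3 = 66.7% | 3/6 = 50.0% |

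In every row, worsening among the a patients abnormal at baseline adds 0.

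**How often a cohort is affected.** If each patient has probability p of an abnormal baseline for a given parameter, independently, the chance of at least one in the cohort is 1 − (1 − p)^n.

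| assumed p | n = 3 | n = 6 |
|---|---|---|
| 0.1 | 27% | 47% |
| 0.3 | 66% | 88% |
| 0.5 | 88% | 98% |
| 0.7 | 97% | >99% |

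**Per-patient count.** SAP 3.9.4 schedules vital signs at 5 times up to 90 minutes and 7 times from 2 to 20 hours. It then schedules them every 4 hours from 24 to 192 hours, which is (192 − 24)/4 + 1 = 43 times. The in-patient total is 5 + 7 + 43 = 55. Take a cohort of 3 and three of these time points. If one patient is high at all three, the table prints 1/3 three times. If three patients are each high once, at different times, it also prints 1/3 three times. The first case is one patient affected and the second is all three. The fever table in 4.5.3 is also by time point and has the same limit.

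**Repeat and unscheduled values.** The 4.1.2 rule plainly drops a repeat at a time point. It does not expressly exclude unscheduled values between time points. Those fall out because a by-time-point table has no place for them, which is an inference from the layout.

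**The case against.** The strongest reply is that this concerns one family of descriptive tables and that the safety report covers the ground elsewhere. Most of that stands.

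- All values, including unscheduled ones, are listed, and laboratory listings carry abnormality flags and change from baseline.
- Mean change is plotted by dose level, and patients abnormal at baseline contribute to it.
- Fever categories do not depend on a normal baseline. SOFA organ scores and clinically significant SpO2 changes are summarized by time point.
- Grade 3-4 laboratory worsening, and clinically significant Grade 1-2 abnormalities, become adverse events.
- Daily laboratory tests and 4-hourly vital signs through Day 7 limit missed peaks in hospital.

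A reader might therefore infer too much by concluding that lower-grade trends and vital-sign peaks have no summary at all, or that the safety report misses them. The SAP does not support that. What these outputs do not give is a per-patient count of worsening outside the adverse event tables. A mean plot can hide one patient's excursion.

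A second reply is that 2/6 is a correct share of the cohort and 2/3 answers a different question. That also stands. A reader might infer that the tables understate toxicity by 20% to 60%. That range is 1 − q for an assumed fraction q normal at baseline between 0.8 and 0.4. Nothing in the SAP fixes q, so it is an illustration and not an error estimate.

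Third, the wording leaves some room. The sentences in 4.5.2 and 4.5.3 are fragments, the table titles would allow a fuller shift table, and 4.1.2 says the table list may be updated. SAP 4.1.2 also excludes missing data from analysis, which could be read as removing unmeasured patients from a percentage. The sentence on denominators is the more specific rule, however, and the methods text names two categories. A programmer following the text would build the narrow table.

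**Conclusion.** The point holds for the laboratory and vital-sign shift tables and no further. As specified, they cannot show worsening from an abnormal baseline, they keep patients who cannot shift in the denominator, they drop repeat values, and they do not show how many patients were ever abnormal. That unscheduled values between visits are left out is inferred from the layout.

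The size depends on how many patients start abnormal, which the SAP does not state. At an assumed 30% per parameter, at least one patient falls outside the categories in 66% of cohorts of 3 and 88% of cohorts of 6. Escalation and the MTD rest on DLTs (SAP 3.1 and Table 1), so no dose decision changes. This is a worthwhile, inexpensive improvement to descriptive safety tables.

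**What to change.** 1. For laboratory tests that can be graded, tabulate baseline CTCAE 4.0 grade against the worst post-dose grade per patient, including repeat and unscheduled values.
2. For other laboratory tests and for vital signs, tabulate low/normal/high at baseline against the worst post-dose category per patient, on the same basis. Say for each parameter which direction counts as worst, or show both. Add the largest change from baseline per patient, because low/normal/high alone does not show a high value that goes higher.
3. Add maximum post-dose temperature per patient to the fever table.
4. Use patients with both a baseline and a post-dose value as the denominator, and print the number in each baseline category. The second part is needed: if all 6 patients are measured, the new denominator still gives 2/6, and only the count of 3 normal at baseline lets the reader see 2/3.
5. State in 4.1.2 that these worst-value tables are an exception to the original-assessment rule and to the default denominator.

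The cost is more programming and slightly longer tables. The data are already collected and listed.
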